## **Abstract**

**Background:** Healthcare professionals are at high risk of developing mental health disorders due to the stress they experience. Therefore, it is essential to offer evidence-based psychotherapeutic interventions to reduce their stress and improve their well-being. This protocol presents a Hybrid Type III study that evaluates the feasibility, acceptability, and sustainability of an online psychotherapy program—MINDxYOU—targeted at healthcare workers. In the context of growing demand for accessible and effective psychological interventions for health professionals, this study aims to test an implementation strategy that facilitates the integration of an evidence-based intervention into routine clinical practice.

**Methods/Design:** This research adopts a Hybrid Type III effectiveness-implementation design, primarily focusing on evaluating implementation strategies in real-world settings while simultaneously collecting data on clinical effectiveness. The study will be conducted in two phases: Phase 1: A pilot study (N=30) at the Regional University Hospital of Málaga. Phase 2: A larger-scale implementation (N=100) within the Andalusian Public Health System (SAS), targeting healthcare professionals providing direct care in hospital and primary care settings. Implementation outcomes to be evaluated include feasibility, acceptability, and sustainability.

**Discussion:** This implementation study aims to provide a framework for addressing barriers and enhancing facilitators for the integration of online interventions into healthcare practice. The ultimate goal is to bridge the gap between research and clinical practice, thereby contributing to the reduction of stress among healthcare professionals.

## 1. Background

Healthcare professionals face a series of stressors inherent to the highly demanding nature of their work, which can negatively impact their psychological well-being and physical health. Stress in these professionals is associated with increased emotional exhaustion, fatigue, and a decline in the quality of care provided to patients. The constant pressure to make quick and accurate decisions, high workload, intense emotions from interacting with critically ill patients, and confronting death and suffering can lead to disorders such as anxiety, depression, and burnout.

Despite growing awareness of the importance of supporting healthcare workers' mental health, traditional stress management interventions such as face-to-face therapy are often inaccessible or unfeasible for these professionals, who have limited time for self-care. There is thus an urgent need for solutions that are not only effective but also accessible and adaptable to the daily realities of these workers.

Various mindfulness-based interventions have shown effectiveness in reducing stress, but most require in-person participation. Digital mindfulness-based interventions—especially unguided ones—have gained attention for their flexibility and potential to be used conveniently by healthcare workers. One major challenge in psychological interventions is the gap between research and practice. Even when proven effective, interventions can take years to be implemented in real-world settings. Implementation science seeks to address this gap by studying barriers and facilitators to adopting new interventions in clinical environments.

MINDxYOU is an online psychotherapy program that integrates strategies such as mindfulness, compassion, acceptance, and spirituality to improve mental health among healthcare professionals. While previous studies have demonstrated its efficacy under controlled conditions, its implementation in real clinical settings requires a thorough evaluation of feasibility, acceptability, and sustainability. Identifying the barriers and facilitators that influence its adoption and continued use is key to ensuring successful integration into the healthcare system.

This study uses a Hybrid Type III design, allowing for simultaneous evaluation of implementation strategies and clinical outcomes. Unlike trials focused solely on efficacy, this approach prioritizes the analysis of factors influencing the program's acceptability and sustainability within health services. Specifically, the study will assess healthcare professionals' willingness to use MINDxYOU, their satisfaction with the platform, and the feasibility of incorporating it into daily clinical practice.

## 2. Research Question and Applicability

What is the feasibility, acceptability, and sustainability of implementing the MINDxYOU program in real healthcare settings, and what is its impact on reducing stress and improving the well-being of healthcare professionals?

This study has high applicability in mental health, particularly in healthcare systems experiencing high stress levels. Its integration into public health institutions could facilitate access to evidence-based interventions aimed at improving the well-being of healthcare professionals. Moreover, its findings will help optimize the implementation of digital therapies, identify barriers and facilitators, and extrapolate its use to other high-stress sectors. Evaluating its sustainability will support broader dissemination and adaptation to different contexts, ensuring long-term impact.

### **3. Hypotheses**

1. Primary hypothesis (implementation): Implementing the MINDxYOU program in healthcare settings will be feasible, acceptable, and sustainable among healthcare professionals.
2. Secondary hypothesis (clinical effectiveness): Participants using the program will experience a significant reduction in perceived stress, anxiety, and depressive symptoms compared to baseline.
3. Adherence hypothesis: Program usage and participant satisfaction will be positively associated with perceived ease of use and perceived effectiveness of the intervention.
4. Barriers and facilitators hypothesis: Factors such as work overload and lack of time may hinder program adoption, while accessibility and the flexibility of the online format will facilitate its integration into the routines of healthcare professionals.

### **4. Objectives**

Primary Objective:

To evaluate the feasibility, acceptability, and sustainability of implementing the MINDxYOU program in real-world healthcare settings.

Secondary Objective:

To assess clinical outcomes of the intervention, including its effects on perceived stress, anxiety levels, and depression symptoms among healthcare professionals.

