### **5. Methodology**

#### **5.1 Study Design**

This study will adopt a Hybrid Type III effectiveness-implementation design, which combines the evaluation of implementation processes with the observation of the clinical outcomes of the intervention. This type of design primarily focuses on implementation strategies (feasibility, acceptability, and sustainability), while clinical outcomes are assessed in a naturalistic way without randomization at the patient level (Proctor et al., 2011).

Study phases:

- Phase 1 – Pilot study (N=30): An initial pilot study will be conducted at the Regional University Hospital of Málaga with a group of healthcare professionals. The program's acceptability will be assessed through surveys and interviews, and its use within the clinical setting will be observed.
- Phase 2 – Expanded study (N=100): In this phase, the program will be implemented at scale within the Andalusian Health Service (SAS), including a broader sample of healthcare professionals from hospitals and primary care centers.

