## 6. Data Analysis

For the implementation analysis, outcomes will be assessed following the framework by Hermes et al. (2019) and Proctor et al. (2011). Passive data will include objective usage metrics (e.g., logins, frequency of use, completed modules, tasks submitted). Quantitative data from questionnaires will be analyzed using appropriate statistical methods, while qualitative data will be gathered through stakeholder interviews.

For the clinical analysis, variables will be described using mean and 95% confidence intervals for normally distributed quantitative variables, or medians and interquartile range for non-normally distributed data. Effectiveness variables (stress, anxiety, and depression) will be compared using paired-samples t-tests.

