## 11. Discussion

This implementation study of the MINDxYOU program provides key insights into the feasibility, acceptability, and sustainability of a digital mental health intervention for healthcare professionals. Findings will evaluate how mindfulness-, compassion-, and acceptance-based strategies can be effectively integrated into real clinical settings (Bauer & Kirchner, 2020).

A key strength of this study lies in its implementation science approach, addressing both barriers and facilitators of adoption in the Andalusian Health Service. Identifying these factors is essential for designing strategies that support the sustainable and scalable use of

MINDxYOU. The Hybrid Type III design advances implementation science by simultaneously assessing clinical effectiveness and contextual influences (Proctor et al., 2011).

Preliminary evidence suggests MINDxYOU can significantly reduce perceived stress and improve healthcare professionals' psychological well-being (López-Del-Hoyo et al., 2025). However, real-world implementation may face challenges, including adherence and acceptance by participants. Results will be essential to evaluate the program's feasibility in busy clinical workflows.

Digital platforms for mental health gained rapid acceptance during the COVID-19 pandemic, representing a paradigm shift in healthcare delivery. Still, questions remain about their long-term quality, accessibility, and effectiveness. This study includes usability and acceptability metrics to empirically evaluate healthcare professionals' engagement and identify factors that could enhance implementation (Bangor et al., 2008).

From a clinical perspective, results may help bridge the gap between research and care, supporting routine use of evidence-based interventions. Findings can inform program adaptations and scalability for other high-stress populations. Ultimately, improving healthcare workers' mental health may also enhance patient care quality. Effective implementation strategies could guide future digital health interventions, benefiting both the workforce and the healthcare system as a whole.

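### Do the causal words in the research question and secondary objective ask for more than a single-group paired t-test can show?

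*Protocol*

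**What the plan says.** Two places in the protocol use causal language for the clinical part. Section 2 asks "what is its impact on reducing stress and improving the well-being of healthcare professionals". The secondary objective in Section 4 is to assess the intervention's clinical outcomes, "including its effects on perceived stress, anxiety levels, and depression symptoms among healthcare professionals".

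Other places attach the label *effectiveness* to the same part. The Abstract describes evaluating implementation strategies "while simultaneously collecting data on clinical effectiveness", Section 6 states "Effectiveness variables (stress, anxiety, and depression) will be compared using paired-samples t-tests", and Section 11 says "The Hybrid Type III design advances implementation science by simultaneously assessing clinical effectiveness and contextual influences".

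The design and the hypothesis are more restrained. Section 5.1 speaks of "the observation of the clinical outcomes of the intervention" and says that "clinical outcomes are assessed in a naturalistic way without randomization at the patient level". Section 3 reads "Secondary hypothesis (clinical effectiveness): Participants using the program will experience a significant reduction in perceived stress, anxiety, and depressive symptoms compared to baseline". Section 10 names the absence of a control group among the limitations.

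**The concern.** A paired t-test on one group estimates the mean difference between two time points. It responds equally to a benefit of the program, natural recovery, a change in workload, or regression to the mean. Regression to the mean is plausible here, because Section 5.6 recruits partly from staff attending occupational stress consultations. A question about *impact* or *effects* calls for a comparison with what would have happened without the program, and this design does not supply one. An SAP that is not shown could not supply it either.

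What would be at stake is the reading of a positive result. A significant fall in perceived stress could satisfy the hypothesis in Section 3 and then, by way of Sections 2 and 4, be reported as an effect of the program.

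**Working it through.** **1. The plan's own figure.** Section 5.5 gives N = 30 for dz = 0.46 and N = 100 for dz = 0.25, with alpha 0.05 and 80% power. Sidedness is not stated.

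- One-sided, exact noncentral t: 31 and 101 needed (normal approximation 30 and 99). Power at the stated N is 79.3% and 79.9%. The stated figures are reproduced to within one participant.
- Two-sided: 40 and 128 needed. Power at the stated N is 68.3% and 69.7%. The stated figures are not reproduced.

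Sidedness is a separate matter. What counts here is that both phases are sized for a within-person change, which is the quantity Section 6 analyses.

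**2. The passages side by side.**

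| Section | What it asks or does | Does a single-group paired test match it? |
|---|---|---|
| 2, research question | impact on stress and well-being | no, as worded |
| 4, secondary objective | clinical outcomes, including effects on three symptoms | main clause yes, subordinate phrase no |
| 3, secondary hypothesis | reduction compared to baseline | yes |
| 5.1, design | observation of outcomes, naturalistic, not randomised | yes |
| 5.5, sample size | paired t-test | yes |
| 6, analysis | paired t-test | yes |
| 10, limitations | no control group | states why attribution is limited |

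The hypothesis, the sample size and the analysis all address the same quantity. Only Section 2 and one phrase in Section 4 go further.

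**3. The label *effectiveness*.** In the Abstract and in Sections 3, 6 and 11 the word echoes the design name, effectiveness-implementation. In Section 6 it serves as a group name for stress, anxiety and depression. These labels do not themselves assert a cause.

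**4. Can the mismatch be given a size?** The smallest observed dz that reaches significance is t(quantile, n − 1)/√n, if all N have both assessments.

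- N = 100: two-sided 1.984/10 = 0.198; one-sided 1.660/10 = 0.166.
- N = 30: two-sided 2.045/5.477 = 0.373; one-sided 1.699/5.477 = 0.310.
- Ratio to the planning dz, two-sided: 0.198/0.25 = 0.79 and 0.373/0.46 = 0.81.
- Ratio to the planning dz, one-sided: 0.166/0.25 = 0.66 and 0.310/0.46 = 0.67.

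These figures show that a modest shift from any cause would be significant. They do not measure the mismatch. The one-sided ratio is close to 1.645/(1.645 + 0.842) = 0.66, which holds for any one-sided 5% test with 80% power, in a randomised trial as much as here. The two-sided ratios are higher only because two-sided power at the stated N is below 80%. No size can be put on regression to the mean either: Section 5.3 sets no minimum stress score, and the protocol gives no expected baseline elevation and no retest interval.

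**5. What rewording would change.** Replacing the causal words with change from baseline leaves the outcomes, N, test and estimates as they are. It would also not be quite clean. Section 2 mentions well-being, but the clinical instruments in Section 5.4 are the PSS, PHQ-9 and GAD-7, and none is named as a well-being measure. A rewording that kept the term would promise a measured change with no instrument attached.

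**The case for a change.** The best case for a change is that objectives govern reporting, so they should match the hypothesis and the test. Section 10 lists the missing control group but does not say what follows from it, and no section states that change from baseline will not be read as an effect of the program. The earlier evidence cited in Sections 1 and 5.7 does not turn this study's before-after change into a causal estimate. The edit would cost almost nothing.

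Most of this is true. Sections 2 and 4 are looser than Section 3, and an author revising the document for another reason could well tighten both phrases and add a caution to Section 6. What does not stand is the step from there to a needed correction. The reason for caution is already disclosed. How a significant before-after change is interpreted is commonly settled in the SAP or the report. Removing *effectiveness* from the Abstract and Sections 3, 6 and 11 while keeping it in the design name would be a matter of taste.

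**Conclusion.** The point is accurate but too slight to require a change. The causal tone is confined to the research question and one phrase of a secondary objective, in a study whose primary aim is implementation. The hypothesis, sample size and analysis consistently target change from baseline, and the protocol says openly that there is neither randomisation nor a control group. No estimate, test or sample size would differ under alternative wording.

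This rests on two assumptions: that the clinical results are reported as Section 3 frames them, as change compared to baseline, and that the limitation in Section 10 is carried into the report. If a report presented the paired result as a demonstrated effect of the program, the fault would lie in that report, and the protocol's own Sections 5.1 and 10 would contradict it.

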### **5. Methodology**

#### **5.1 Study Design**

This study will adopt a Hybrid Type III effectiveness-implementation design, which combines the evaluation of implementation processes with the observation of the clinical outcomes of the intervention. This type of design primarily focuses on implementation strategies (feasibility, acceptability, and sustainability), while clinical outcomes are assessed in a naturalistic way without randomization at the patient level (Proctor et al., 2011).

Study phases:

- Phase 1 – Pilot study (N=30): An initial pilot study will be conducted at the Regional University Hospital of Málaga with a group of healthcare professionals. The program's acceptability will be assessed through surveys and interviews, and its use within the clinical setting will be observed.
- Phase 2 – Expanded study (N=100): In this phase, the program will be implemented at scale within the Andalusian Health Service (SAS), including a broader sample of healthcare professionals from hospitals and primary care centers.

## 5.2 Participants

The study sample will consist of healthcare professionals working in clinical settings (hospitals and primary care centers) within the Andalusian Health Service (SAS). Participants may include doctors, nurses, nursing assistants, social workers, physiotherapists, psychologists, ambulance technicians, and healthcare students.

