## 5.3 Inclusion and Exclusion Criteria

Inclusion criteria:

(1) Being a current healthcare professional (2) Aged between 18 and 70 years (3) Ability to understand Spanish (4) Digital literacy and access to a smartphone, tablet, or computer with internet access (5) Continuity in the same workplace for at least 6 months (6) Signing the informed consent form

Exclusion criteria: (1) Diagnosis of severe mental illness (2) Suicidal ideation (3) Substance abuse or related disorders

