### **5.6 Procedure**

Recruitment strategies will include posters and brochures in hospitals and primary care centers, as well as presentations in group sessions with healthcare professionals, including those attending occupational stress consultations. Email invitations will include a brief explanation of the study and a web link to the platform. Participants will be required to submit signed informed consent electronically. Eligibility will be verified, and those meeting inclusion criteria will be formally enrolled. Participants will receive a welcome email with platform login credentials. Instructions on how to use the platform will be provided in the welcome module.

Participants will be assessed on all study variables every 8 weeks. Usability (SUS) will be assessed after completing Modules 1 and 4. Platform usage will be tracked (logins, completed modules, submitted tasks).

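### Does listing healthcare students in section 5.2 conflict with the requirement in section 5.3 to be a current healthcare professional?

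*Protocol*

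**What the plan says.** Section 5.2 has two sentences. The first sets the population: "The study sample will consist of healthcare professionals working in clinical settings (hospitals and primary care centers) within the Andalusian Health Service (SAS"). The second lists who may be in it: "Participants may include doctors, nurses, nursing assistants, social workers, physiotherapists, psychologists, ambulance technicians, and healthcare students".

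Section 5.3 then opens its inclusion criteria with "1) Being a current healthcare professional (2) Aged between 18 and 70 years". It names no occupation. Its fifth criterion requires at least six months in the same workplace.

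Section 5.6 makes these criteria decisive for entry: "Eligibility will be verified, and those meeting inclusion criteria will be formally enrolled".

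Other sections describe the population only in general terms. The Abstract describes Phase 2 as "targeting healthcare professionals providing direct care in hospital and primary care settings". Section 5.1 gives the pilot as "An initial pilot study will be conducted at the Regional University Hospital of Málaga with a group of healthcare professionals" and the expanded study as "including a broader sample of healthcare professionals from hospitals and primary care centers". The secondary objective in section 4 concerns clinical outcomes, "including its effects on perceived stress, anxiety levels, and depression symptoms among healthcare professionals". The research question (section 2) and the primary hypothesis (section 3) use the same general term.

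**The concern.** A student is not usually called a professional, and the word *current* in criterion 1 can be taken to mean someone already qualified and practising. On that reading, section 5.2 admits a group that section 5.3 shuts out. Section 5.6 ties enrolment to section 5.3, so the section that names students does not govern entry, and the section that governs entry does not name them.

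The possible consequence is inconsistent enrolment. One person checking eligibility might refuse a student on the literal wording of criterion 1, and another might accept the same student on the strength of the list. The study has no control group (section 10), so its results describe whoever is enrolled. The primary hypothesis is stated for healthcare professionals, and the fourth hypothesis in section 3 concerns work overload and fitting the program into professionals' routines. A sample with an unclear share of students would answer those questions for a less clearly defined population. Eligibility is also a protocol matter, so a separate analysis plan would not be expected to settle it.

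**Working it through.** There is no figure to reproduce. The check is a comparison of the texts.

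1. **Where students appear.** They appear only in section 5.2, as the last of eight groups in the list.

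2. **What the list does.** It follows at once on the sentence that fixes the sample as healthcare professionals in clinical settings, and it spells out who the participants may be. The ordinary reading of two such sentences is that the second illustrates the term in the first. Criterion 1 uses the same term in the next section. Taken together, section 5.2 says who counts and section 5.3 sets the conditions they must meet. On this reading nothing contradicts.

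3. **What *current* excludes.** Its usual contrast is with former or retired staff. Nothing in the protocol sets it against people in training.

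4. **What the silence elsewhere shows.** Six places state the question, hypothesis, objective, target, phases or criterion without mentioning students: the Abstract and sections 2, 3, 4, 5.1 and 5.3. None of them names any of the other seven groups in the section 5.2 list either. If silence excluded students, it would exclude doctors and nurses too, which nobody would argue. The silence therefore carries no weight in either direction.

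5. **Whether direct care excludes students.** The Abstract's phrase for Phase 2 does not by itself rule out a student working in a clinical setting.

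6. **How many could be affected.** The protocol gives no expected number. Every participant, student or not, must meet the six-month workplace criterion, which limits how many students could enter.

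7. **What depends on the answer.** Section 5.5 derives N = 30 from an assumed effect of dz = 0.46 and N = 100 from dz = 0.25, both for a paired t-test. Professional category enters neither calculation. Section 6 compares stress, anxiety and depression by paired t-tests within participants, and that analysis is the same whether or not students are enrolled. With no second arm, admitting or refusing a student cannot unbalance a comparison.

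The answer bears only on the description of the sample. The protocol gives no figure on how students' outcomes would differ from those of staff, so no numerical effect can be derived.

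**The case for a change.** The strongest case for a change is that the protocol never says in words that the list defines the term. Someone who applies criterion 1 literally and someone who relies on section 5.2 could both claim to be following the protocol. Recruitment covers hospitals and primary care centers, where a single reading of eligibility is desirable. Section 7 counts changes in eligibility among the major modifications that need ethics approval, so the protocol itself treats eligibility as important. Clarifying the wording would cost almost nothing.

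Part of this stands. The term has no express definition, and who may enter is for the protocol to say. The rest is weaker. The picture of assessors disagreeing is conjecture: section 5.6 says that eligibility is verified, but not that several people do it or that they work without a shared understanding. The literal reading of criterion 1 requires setting aside an explicit list in the section just before it. A low cost makes a clarification harmless, but it does not show that the study's results would be any sounder for it.

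**Conclusion.** The concern does not call for a change. The two sections are compatible on their natural reading: the groups in section 5.2, students included, illustrate who counts as a healthcare professional, and section 5.3 adds the conditions for entry. What remains is an unstated definition that study staff can fill sensibly from the preceding section.

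The consequence is minor. Both sample sizes, the outcomes and the tests stay as they are, and a single-arm study has no between-group comparison to bias. Any effect is confined to the make-up of the sample, and reporting participants by occupation would show that to a reader.

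This conclusion rests on two assumptions. The first is that the list was meant as it reads. The second is that students form a modest part of the sample, which the six-month workplace criterion makes likely but which the protocol does not quantify. If the sponsor revises the protocol for other reasons, a clause in criterion 1 saying whether the section 5.2 list defines the term would be a courtesy to the reader. The plan is sound without it.
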